12.5.8.4. Recording of AEs related to COVID-19

For COVID-19 infection-related AEs, sites should follow routine AE/SAE processes as outlined in the protocol, using the following terms according to the latest COVID-19 case definitions criteria in effect at the institution:

- Suspected COVID-19 case
- Probable COVID-19 case
- Confirmed COVID-19 case

If subject is diagnosed with COVID-19 as above, report each occurrence in the COVID-19 Coronavirus Infection Assessment form. In addition, complete for each occurrence as AE on the Non-Serious Adverse form or as SAE on the Expedited Adverse Event Report form (depending on the level of seriousness as assessed by the Principal Investigator or delegate). Please also report the relevant medications related to this event. Follow the guidelines applicable for those forms on how to record COVID-19.

12.5.9. Reporting of serious adverse events, pregnancies, and other events

12.5.9.1. Prompt reporting of serious adverse events, pregnancies, and other events to GSK Biologicals

SAEs that occur in the time period defined in Section 12.5.8 will be reported promptly to GSK within the timeframes described in [Table 17](#), once the investigator determines that the event meets the protocol definition of a SAE.

Pregnancies that occur in the time period defined in Section 12.5.8 will be reported promptly to GSK within the timeframes described in [Table 17](#), once the investigator becomes aware of the pregnancy.

AESIs that occur in the time period defined in Section 12.5.8 will be reported promptly to GSK within the timeframes described in [Table 17](#), once the investigator determines that the event meets the protocol definition of a AESIs.

12.5.9.2. SAEs requiring expedited reporting to GSK Biologicals

Once an investigator becomes aware that a SAE has occurred in a study subject, the investigator (or designate) must complete the information in the electronic Expedited Adverse Events Report **WITHIN 24 HOURS**. The report will always be completed as thoroughly as possible with all available details of the event. Even if the investigator does not have all information regarding a SAE, the report should still be completed within 24 hours. Once additional relevant information is received, the report should be updated **WITHIN 24 HOURS**.

The investigator will always provide an assessment of causality at the time of the initial report. The investigator will be required to confirm the review of the SAE causality by ticking the 'reviewed' box in the electronic Expedited Adverse Events Report within 72 hours of submission of the SAE.

12.5.9.3. Back-up system in case the electronic reporting system does not work

If the electronic reporting system does not work, the investigator (or designate) must complete, then date and sign a paper Expedited Adverse Events Report and fax it to the Study Contact for Reporting SAEs (refer to the [Sponsor Information](#)) or to GSK Biologicals Clinical Safety and Pharmacovigilance department within 24 hours.

This back-up system should only be used if the electronic reporting system is not working and NOT if the system is slow. As soon as the electronic reporting system is working again, the investigator (or designate) must complete the electronic Expedited Adverse Events Report within 24 hours. The final valid information for regulatory reporting will be the information reported through the electronic SAE reporting system.

12.5.9.4. Completion and transmission of pregnancy reports to GSK Biologicals

Once the investigator becomes aware that a subject is pregnant, the investigator (or designate) must complete the required information onto the electronic pregnancy report within 24 hours.

Note: Conventionally, the estimated gestational age (EGA) of a pregnancy is dated from the first day of the last menstrual period (LMP) of the cycle in which a woman conceives. If the LMP is uncertain or unknown, dating of EGA and the estimated date of delivery (EDD) should be estimated by ultrasound examination and recorded in the pregnancy report.

12.5.9.5. Reporting of AESI's to GSK Biologicals

Once an AESI is diagnosed (serious or non-serious) in a study subject, the investigator (or designate) must complete the information in the electronic Expedited Adverse Events Report **WITHIN 24 HOURS** after he/she becomes aware of the diagnosis. The report allows specify that the event is an AESI and whether it is serious or non-serious. The report will always be completed as thoroughly as possible with all available details of the event, in accordance with the AESIs standard questionnaire provided. Even if the investigator does not have all information regarding an AESI, the report should still be completed within 24 hours. Once additional relevant information is received, the report should be updated **WITHIN 24 HOURS**.

The investigator will always provide an assessment of causality at the time of the initial report. The investigator will be required to confirm the review of the AESI causality by ticking the 'reviewed' box in the electronic Expedited Adverse Events Report within 72 hours of submission of the AESI.

Refer to Section 12.5.9.3 for back-up system in case the electronic reporting system does not work.

12.5.10. Updating of SAE, pregnancy, and AESI information after removal of write access to the subject's eCRF

When additional SAE, pregnancy, or AESI information is received after removal of the write access to the subject's eCRF, new or updated information should be recorded on the appropriate paper report, with all changes signed and dated by the investigator. The updated report should be faxed to the Study Contact for Reporting SAEs (refer to the [Sponsor Information](#)) or to GSK Biologicals Clinical Safety and Pharmacovigilance department within the designated reporting time frames specified in [Table 17](#).

12.5.11. Follow-up of adverse events, serious adverse events, and pregnancies

12.5.11.1. Follow-up of adverse events and serious adverse events

12.5.11.1.1. *Follow-up during the study*

After the initial AE/SAE report, the investigator is required to proactively follow each subject and provide additional relevant information on the subject's condition to GSK Biologicals (within 24 hours for SAEs; refer to [Table 17](#)).

All SAEs and AESIs (serious or non-serious) documented at a previous visit/contact and designated as not recovered/not resolved or recovering/resolving will be reviewed at subsequent visits/contacts until the last visit/contact of the subject.

All AEs documented at a previous visit/contact and designated as not recovered/not resolved or recovering/resolving will be reviewed at subsequent visits/contacts until the last visit/contact of the subject.

12.5.11.1.2. *Follow-up after the subject is discharged from the study*

The investigator will follow subjects:

- with SAEs, AESIs (serious or non-serious), or subjects withdrawn from the study as a result of an AE, until the event has resolved, subsided, stabilized, disappeared, or until the event is otherwise explained, or the subject is lost to follow-up.
- with other non-serious AEs, until one year after LSLV or if the subject is lost to follow-up.

If the investigator receives additional relevant information on a previously reported SAE, he/she will provide this information to GSK Biologicals using a paper/electronic Expedited Adverse Events Report and/or pregnancy report as applicable.

GSK Biologicals may request that the investigator performs or arranges the conduct of additional clinical examinations/tests and/or evaluations to elucidate as fully as possible the nature and/or causality of the AE or SAE. The investigator is obliged to assist. If a subject dies during participation in the study or during a recognized follow-up period, GSK Biologicals will be provided with any available post-mortem findings, including histopathology.

12.5.11.2. Follow-up of pregnancies

Pregnant subjects will be followed to determine the outcome of the pregnancy. At the end of the pregnancy, whether full-term or premature, information on the status of the mother and child will be forwarded to GSK Biologicals using the paper pregnancy follow-up report/electronic pregnancy report and the Expedited Adverse Events Report if applicable. Generally, the follow-up period doesn't need to be longer than 6 to 8 weeks after the estimated date of delivery.

Regardless of the reporting period for SAEs for this study, if the pregnancy outcome is a SAE, it should always be reported as SAE.

The following should always be considered as SAE.

- Spontaneous pregnancy loss, including:
 - spontaneous abortion, (spontaneous pregnancy loss before/at 22 weeks of gestation)
 - ectopic and molar pregnancy
 - stillbirth (intrauterine death of fetus after 22 weeks of gestation).
- Any early neonatal death (i.e. death of a live born infant occurring within the first 7 days of life).
- Any congenital anomaly or birth defect [as per Metropolitan Atlanta Congenital Defects Program [[MACDP](#)] guidelines] identified in the offspring of a study subject (either during pregnancy, at birth or later) regardless of whether the foetus is delivered dead or alive. This includes anomalies identified by prenatal ultrasound, amniocentesis or examination of the products of conception after elective or spontaneous abortion.

12.6. Appendix 6: Contraceptive guidance and collection of pregnancy information

12.6.1. Definitions

12.6.1.1. Woman of Childbearing Potential (WOCBP)

A woman is considered fertile following menarche and until becoming post-menopausal unless permanently sterile (see below)

12.6.1.1.1. Women in the following categories are not considered WOCBP

- Premenarchal

Menarche is the onset of menses for the first time in a young female and is preceded by several changes associated with puberty including breast development and pubic hair growth. Menarche usually occurs within 1-2 years of breast development, thelarche. However, a young female can become pregnant before her first menses. Thus, a conservative definition of non-childbearing potential in a pre-menarcheal female is a young female who has not yet entered puberty as evidenced by lack of breast development (palpable glandular breast tissue).

- Premenopausal female with ONE of the following:
 - Documented hysterectomy
 - Documented bilateral salpingectomy
 - Documented bilateral oophorectomy

Note: Documentation can come from the site personnel's: review of subject's medical records, medical examination, or medical history interview.

- Postmenopausal female

A postmenopausal state is defined as no menses for 12 months without an alternative medical cause. A high follicle stimulating hormone (FSH) level in the postmenopausal range may be used to confirm a postmenopausal state in women not using hormonal contraception or hormonal replacement therapy (HRT). However, in the absence of 12 months of amenorrhea, a single FSH measurement is insufficient.

- Females on HRT and whose menopausal status is in doubt will be required to use 1 of the non-hormonal highly effective contraception methods if they wish to continue their HRT during the study. Otherwise, they must discontinue HRT to allow confirmation of postmenopausal status before study enrolment.

12.6.2. Contraception guidance

- Female subjects of childbearing potential are eligible to participate if they agree to use an adequate contraception consistently and correctly according to the methods listed in GSK list of highly effective contraceptive methods as described in [Table 30](#).

Table 30 Highly Effective Contraceptive Methods

Highly Effective Contraceptive Methods That Are User Dependent ^a
 
Failure rate of <1% per year when used consistently and correctly.

Combined (oestrogen- and progestogen-containing) hormonal contraception associated with inhibition of ovulation^b
 
 oral intravaginal transdermal

Progestogen-only hormonal contraception associated with inhibition of ovulation^b
 
 injectable

Highly Effective Methods That Are User Independent
 
 Implantable progestogen-only hormonal contraception associated with inhibition of ovulation^b Intrauterine device (IUD) Intrauterine hormone-releasing system (IUS) bilateral tubal occlusion

Vasectomized partner
 
(A vasectomized partner is a highly effective contraception method provided that the partner is the sole male sexual partner of the WOCBP and the absence of sperm has been confirmed. If not, an additional highly effective method of contraception should be used.)
 
Male partner sterilization prior to the female subject's entry into the study, and this male is the sole partner for that subject,
 
(The information on the male sterility can come from the site personnel's review of the subject's medical records; medical examination and/or semen analysis, or medical history interview provided by her or her partner).

Sexual abstinence
 
(Sexual abstinence is considered a highly effective method only if defined as refraining from heterosexual intercourse during the entire period of risk associated with the study drug. The reliability of sexual abstinence needs to be evaluated in relation to the duration of the study and the preferred and usual lifestyle of the subject.)

NOTES:

- Typical use failure rates may differ from those when used consistently and correctly. Use should be consistent with local regulations regarding the use of contraceptive methods for subjects in clinical studies.
- Hormonal contraception may be susceptible to interaction with the study drug, which may reduce the efficacy of the contraceptive method. In this case 2 highly effective methods of contraception should be utilised during the treatment period and for at least 2 months after the last dose of study treatment.

12.6.3. Collection of pregnancy information**12.6.3.1. Female Subjects who become pregnant**

- Investigator will collect pregnancy information on any female subject, who becomes pregnant while participating in this study.
- Information will be recorded on the appropriate form and submitted to GSK within 24 hours of learning of a subject's pregnancy.
- Subject will be followed to determine the outcome of the pregnancy. The investigator will collect follow-up information on subject and neonate, which will be forwarded to GSK. Generally, follow-up will not be required for longer than 6 to 8 weeks beyond the estimated delivery date.
- Any termination of pregnancy will be reported, regardless of fetal status (presence or absence of anomalies) or indication for procedure.
- While pregnancy itself is not considered to be an AE or SAE, any pregnancy complication or elective termination of a pregnancy will be reported as an AE or SAE.
- A spontaneous abortion is always considered to be an SAE and will be reported as such.
- Any SAE occurring as a result of a post-study pregnancy which is considered reasonably related to the study treatment by the investigator, will be reported to GSK as described in [12.5.9](#). While the investigator is not obligated to actively seek this information in former study subjects, he or she may learn of an SAE through spontaneous reporting.

Any female subject who becomes pregnant while participating will discontinue study treatment.

12.7. Appendix 7: Definition of medical device AE, adverse device effect (ADE), serious adverse device effect (SADE) and unanticipated SADE (USADE)**12.7.1. Definition of medical device AE and adverse device effect (ADE)**

- Medical device AE is any untoward medical occurrence, in a clinical study participant, users, or other persons, temporally associated with the use of study intervention whether or not considered related to a medical device. An AE can therefore be any unfavorable and unintended sign (including an abnormal laboratory finding), symptom, or disease (new or exacerbated) temporally associated with the use of a medical device. This definition includes events related to the medical device or comparator and events related to the procedures involved.
- An adverse device effect (ADE) is an AE related to the use of a medical device. This definition includes any AE resulting from:
 - insufficient or inadequate instructions for use (i.e. user error), or
 - any malfunction of a medical device, or
 - intentional misuse of the medical device.

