4. OBJECTIVE(S) AND ENDPOINT(S)

Table 6 Study objectives and endpoints (Amended 11 October 2022)

Objectives	Endpoints
Primary	
To assess the safety and tolerability of rMenB+OMV NZ and MenACWY, when administered concomitantly or alone, in healthy subjects 16-18 years of age.	
 • The frequencies and percentages of subjects with solicited local (i.e., injection site pain, erythema, swelling, induration) and systemic (i.e., fever [temperature $\geq 38.0^{\circ}\text{C}/100.4^{\circ}\text{F}$], nausea, fatigue, myalgia, arthralgia, headache) adverse events (AEs) during the 7 days (including the day of vaccination) following the first (Visit 1, Day 1/Month 0), the second (Visit 3, Month 2) and the third (Visit 4, Month 3) vaccination for all groups. • The frequencies and percentages of subjects with any unsolicited AEs (including all SAEs), AEs leading to withdrawal and medically attended AEs during the 30 days (including the day of vaccination) following the first (Visit 1, Day 1/Month 0), the second (Visit 3, Month 2) and the third (Visit 4, Month 3) vaccination for all groups. • The frequencies and percentages of subjects with SAEs, AEs leading to withdrawal, and medically attended AEs, throughout the study period (Day 1/Month 0 to Month 9). • The frequencies and percentages of subjects (who received rMenB+OMV NZ) with AESI throughout the study period (Day 1/Month 0 to Month 9). • Among subjects who are followed for 12 months after their last dose: 
 ○ The frequencies and percentages of subjects with

CONFIDENTIAL

205419 (MENB REC 2ND GEN-045 (V72_79))

Protocol Amendment 7 Final

Objectives	Endpoints
	
SAEs, AEs leading to withdrawal, between SFU 5 (Month 9) and SFU 7 (Month 15).
 
The frequencies and percentages of subjects (who received rMenB+OMV NZ) with AESI between SFU 5 (Month 9) and SFU 7 (Month 15).

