12.5.1.3. Events NOT Meeting the AE Definition

- Situations where an untoward medical occurrence did not occur (e.g. social and/or convenience admission to a hospital, admission for routine examination).
- Anticipated day-to-day fluctuations of pre-existing disease(s) or condition(s) present or detected at the start of the study that do not worsen.
- Pre-existing conditions or signs and/or symptoms present in a subject prior to the first study vaccination. These events will be recorded in the medical history section of the eCRF.
- Medical or surgical procedures (e.g. endoscopy, appendectomy); the condition that leads to the procedure is an AE/SAE.

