12.5.7. Events or outcomes not qualifying as adverse events or serious adverse events

12.5.7.1. Pregnancy

Female subjects who are pregnant or lactating at the time of vaccination must not receive additional doses of study vaccines but may continue other study procedures at the discretion of the investigator.

While pregnancy is not considered an AE or SAE, any adverse pregnancy outcome or complication or elective termination of a pregnancy for medical reasons will be recorded and reported as an AE or a SAE.

Note: The pregnancy should always be recorded on an electronic pregnancy report.

The following should always be considered as SAE and will be reported as described in Sections 12.5.9.1 and 12.5.9.4:

- Spontaneous pregnancy loss, including:
 - spontaneous abortion, (spontaneous pregnancy loss before/at 22 weeks of gestation)

- ectopic and molar pregnancy
- stillbirth (intrauterine death of foetus after 22 weeks of gestation).

Note: the 22 weeks' cut-off in gestational age is based on WHO-ICD 10 noted in the EMA Guideline on pregnancy exposure [[EMA](#), 2006]. It is recognized that national regulations might be different.

- Any early neonatal death (i.e. death of a live born infant occurring within the first 7 days of life).
- Any congenital anomaly or birth defect identified in the offspring of a study subject (either during pregnancy, at birth or later) regardless of whether the foetus is delivered dead or alive. This includes anomalies identified by prenatal ultrasound, amniocentesis or examination of the products of conception after elective or spontaneous abortion.

Furthermore, any SAE occurring as a result of a post-study pregnancy AND considered by the investigator to be reasonably related to the study vaccines will be reported to GSK Biologicals as described in Section [12.5.9](#). While the investigator is not obligated to actively seek this information from former subjects, he/she may learn of a pregnancy through spontaneous reporting.

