5.5.1.3. Analysis of Unsolicited Adverse Events

All safety analyses will be performed using the Exposed set.

This analysis applies to all AEs occurring during the study, judged either as probably related, possibly related, or not related to vaccination by the investigator, recorded in AE eCRF, with a start date on or after the date of first vaccination. All AEs starting prior to the first vaccination will only be listed. The original verbatim terms used by investigators to identify AEs in the eCRFs will be mapped to preferred terms using the MedDRA dictionary. The AEs will then be grouped by MedDRA preferred terms into frequency tables according to system organ class.

All reported AEs, as well as AEs judged by the investigator as at least possibly related to study vaccine, will be summarized according to system organ class and preferred term within system organ class. These summaries will be presented by vaccination group and by interval of study observation. When an AE occurs more than once for a subject, the maximal severity and strongest relationship to the group will be counted.

Separate summaries will be produced for the following categories:

- Serious adverse events (SAEs)
- Adverse Events of Special Interest (AESIs) for subjects who received rMenB+OMV NZ

- Adverse events that are possibly or probably related to vaccine.
- Adverse event leading to withdrawal with relationship to COVID-19.
- Adverse events leading to a medically attended visit.

The frequencies and percentages of subjects who reported at least one immediate unsolicited adverse event (i.e., reactions that occurred during the first 30 minutes after any vaccination that have been flagged as immediate in the eCRF and have not been reported in the eDiary) following any study vaccination will be reported by study group.

Data listings of all AEs will be provided by subject. In addition, AEs in the categories above will be provided as listed data.

Between groups assessment

No statistical tests for between-group comparisons will be performed.

- The percentages of subjects with any unsolicited AEs (including all SAEs) during the 30 days (including the day of vaccination) following the first (Visit 1), the second (Visit 3) and the third (Visit 4) vaccination for all groups will be calculated.

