10.1.2.4. Unsolicited adverse events

Unsolicited adverse event summaries are including serious adverse events unless specified otherwise.

Missing severity, relationship with study vaccine, and outcome of unsolicited adverse events will not be replaced and will appear as 'UNKNOWN' in all statistical output.

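### Protocol 12.5.7.1 and 12.6.3.1 give different rules for when an elective pregnancy termination is an AE or SAE, so a non-medical termination is counted or not depending on the section a site follows

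*Protocol*

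**What the plan says.** Two sections of the protocol appendices deal with elective termination.

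- Section 12.5.7.1 (Pregnancy) sits under a heading for events that do not qualify as AEs or SAEs. It states that pregnancy is not itself an AE, then lists exceptions. One exception is that "elective termination of a pregnancy for medical reasons will be recorded and reported as an AE or a SAE".
- Section 12.6.3.1 (Female Subjects who become pregnant) also starts from pregnancy not being an AE, but says that "any pregnancy complication or elective termination of a pregnancy will be reported as an AE or SAE". It does not carry the medical-reasons limit.

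A separate bullet in 12.6.3.1 covers reporting of the pregnancy outcome: "Any termination of pregnancy will be reported, regardless of fetal status (presence or absence of anomalies) or indication for procedure".

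Two other places bear on the question. Section 12.5.1.3 lists, among events that are not AEs, "Medical or surgical procedures (e.g. endoscopy, appendectomy); the condition that leads to the procedure is an AE/SAE". The lists of pregnancy outcomes that are always SAEs, in 12.5.7.1 and 12.5.11.2, do not include elective termination.

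The affected measures are primary. Protocol section 4 lists "The frequencies and percentages of subjects with SAEs, AEs leading to withdrawal, and medically attended AEs, throughout the study period (Day 1/Month 0 to Month" (the window closes at Month 9), and also "The frequencies and percentages of subjects with any unsolicited AEs (including all SAEs), AEs leading to withdrawal and medically attended AEs during the 30 days" after each vaccination. In the SAP, section 10.1.2.4 adds that "Unsolicited adverse event summaries are including serious adverse events unless specified otherwise".

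**The concern.** A subject who has an elective termination for a non-medical reason has no AE under 12.5.7.1 and has an AE, possibly an SAE, under 12.6.3.1. Two sites with the same event can enter different data while each follows a section of the protocol. The tables would then mix two definitions, and nothing in the SAP would bring them back to one.

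What is at stake is the consistency of descriptive primary safety percentages. The medically attended AE percentage is most exposed. Section 12.5.8.3.2 defines a medically attended AE as one that leads to a visit to a healthcare provider, so a termination recorded as an AE would normally qualify.

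**Working it through.** **Step 1: the two rules side by side**

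| Event | 12.5.7.1 | 12.6.3.1 |
|---|---|---|
| Elective termination, medical reason | AE or SAE | AE or SAE |
| Elective termination, no medical reason | Not an AE | AE or SAE |
| Any termination, pregnancy reporting | Not addressed | Reported regardless of indication |

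The sections agree on the first row and differ on the second. The third row is a separate duty in its own bullet, so the AE/SAE bullet of 12.6.3.1 cannot be read as meaning only the pregnancy report.

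**Step 2: which percentages can move**

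- *Medically attended AEs, Day 1 to Month 9.* These move if the termination is recorded as an AE and involved a healthcare visit. The window is long. Section 6.1 requires contraception until 2 months after the vaccination series. With the last dose at Month 3 this is about Month 5, and collection continues for about 4 more months to Month 9. The exclusion in 6.2.4 of females planning to stop contraception lowers the risk but does not remove it.
- *SAEs, Day 1 to Month 9.* These move only if the event meets a criterion in 12.5.2. Section 12.6.3.1 says AE or SAE, and elective termination is not on the always-SAE lists.
- *Unsolicited AEs within 30 days of a dose.* These move only if the termination falls in that window. Section 8.2.5 requires a negative pregnancy test before each dose, so this is a narrow route.

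**Step 3: size per subject**

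The plan states no pregnancy, termination or SAE rate, so there is no figure of its own to reproduce on this point. The denominator can be checked. Section 10.1.2 targets 250 evaluable subjects per group with 20% drop-out: 250 / 0.80 = 312.5, rounded up to 313, against the 315 planned. I take 315 as the approximate size of each group in the Exposed Set.

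Shift in percentage points = 100 x k / N, where k is the number of affected subjects with no other event of the same category.

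- k = 1: 100 x 1/315 = 0.32
- k = 2: 100 x 2/315 = 0.63
- k = 3: 100 x 3/315 = 0.95
- k = 1 with N = 250: 100 x 1/250 = 0.40

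**Step 4: how many, by assumption only**

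Assume about half of each group is female (157) and that each has a 0.1% to 2% chance of a non-medical elective termination by Month 9. Neither figure is in the documents.

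- Low: 157 x 0.001 = 0.16 subjects per group; 100 x 0.157/315 = 0.05 points
- High: 157 x 0.02 = 3.14 subjects per group; 100 x 3.14/315 = 1.0 point

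This is an upper reading of the shift, because it supposes that none of these subjects has another qualifying event and that every site follows 12.6.3.1.

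**The case against.** The best defence is that the sections are not strictly incompatible: a site that records every elective termination as an AE satisfies both. But that reading leaves the limit in 12.5.7.1 with no purpose, and nothing tells a site to prefer it. A site that reads 12.5.7.1 alone will record nothing on the AE page.

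A second defence is that the consequence is small. This stands. The events should be few, no rate is given, and SAP 5.5.1.3 states that "No statistical tests for between-group comparisons will be performed". Study success in protocol section 4 depends only on the two immunogenicity objectives.

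Three stronger readings are tempting, and the documents do not support them.

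- A reader might infer that each such termination adds to the SAE percentage, and that with few SAEs the relative change would be large. This presumes that every event is classed as serious, which 12.6.3.1 does not say. Any relative change would also need a baseline SAE count, and the plan gives none.
- A reader might infer a distortion of the between-group comparison. Randomization by minimization accounts for center (7.2.2.2.1), and those who evaluate endpoints are blinded (7.3). A site's choice of section should therefore apply alike to all three groups. The result is noise, not a directional bias.
- A reader might infer that the broader rule in 12.6.3.1 is plainly a mistake. Its neighbouring bullet disregards indication, so wide capture may have been intended. Section 12.5.1.3 favours the narrower rule but does not settle the matter.

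**Conclusion.** The inconsistency is real and is in current text. The same event is or is not an AE depending on the section followed, and it can reach a primary safety percentage, mainly medically attended AEs to Month 9. The size that rests on the documents is 0.32 points per affected subject in a group of 315, provided that she has no other qualifying event. The range of 0.05 to 1.0 point per group rests on assumed rates and shows only the order of magnitude. No safety hypothesis is tested and no non-inferiority conclusion can change. It is a low-priority correction of a reporting definition.

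**What to change.** 1. **Protocol.** Reconcile 12.5.7.1 and 12.6.3.1 to a single rule. Carrying the medical-reasons limit into the AE/SAE bullet of 12.6.3.1 fits 12.5.1.3, under which a procedure is not itself an AE. If the sponsor intends the broader rule, remove the limit from 12.5.7.1 instead. Either way, state that seriousness is decided by 12.5.2.
2. **Pregnancy report.** Keep the bullet that requires every termination to be reported, so that no information is lost. Confirm that the report records the indication, since the documents do not say and the rule cannot be applied without it.
3. **SAP 5.5.1.3.** Add one line that applies the chosen rule to the AE, medically attended AE and SAE tables, whichever section a site followed. Under the narrower rule, non-medical elective terminations are listed and not counted.

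The cost is one phrase in the protocol, a cross-reference to 12.5.2 and one SAP sentence. If data collection is already complete, the SAP line is enough to make the tables consistent, provided that the indication is available. The narrower rule is then the easier to apply, because it only removes recorded events. The broader rule would require adding events from the pregnancy reports.
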